# 5.4 Time and Events Table

# PRE-TREATMENT ASSESSMENTS

Assessments	Prior to Registration	Prior to Treatme
	(calendar days)	(calendar days)
History and physical exam	30	
Zubrod performance status	30	
Tumor measurements	30	
Rad Onc exam	30	
Med Onc exam	30	
CBC	30	
CMP	30	
Thyroid function test	30	
AM cortisol, ACTH	30	
Urinalysis	30	
Serum pregnancy test if applicable	3	
Baseline Chest X-Ray	30	
Baseline EKG	30	
Cytology/Pathology Report confirming NSCLC	90	
Whole body FDG- PET/CT (base of skull to mid-thigh)	60	
CT chest with contrast and include adrenals*	60	
MRI of brain (CT if MRI contraindicated)	60	
Pulmonary function testing (PFTs/DLCO)	90	
Informed consent	Within 30 days including Day of registration	
Specimen collection for banking		If patient consents: S Section 9.

\* Patients do not need to have a separate CT of chest and upper abdomen with contrast if FDG-PET/CT imaging includes a high quality CT chest with contrast

# ASSESSMENTS DURING CONCURRENT TREATMENT

Assessments	Weekly (+/- 3 days)	At week 1 and 5 only (+/- 7 days)
Performance status	X	
CMP	X 	
Thyroid function test		X
Adrenal function test		X
Rad Onc Evaluation	X	
Med Onc evaluation		X 
Adverse event evaluation	X	
Specimen collection for banking		$X_3$

<sup>1 Biweekly

<sup>2 Testing does not need to be repeated if performed within 7 days of starting protocol therapy.

<sup>3Day 1 and Day 42

#### ASSESSMENTS DURING CONSOLIDATIVE DURVALUMAB TREATMENT

Assessments	Every month at infusion	Every 3 months
Physical examination including vital signs (blood pressure, weight)	X	
Zubrod performance status	X	
CMP	X	
Thyroid function (TSH, T3 and T4);		Every 2 months
AM cortisol, ACTH		Every 2 months
Serum or urine Pregnancy test	X 	
AE evaluation	X	
CT of chest with contrast and include adrenals		X 
Pulmonary function testing (PFTs/DLCO)		X 
Blood collection for banking		X 

<sup>1 Every 6 weeks

<sup>2After completion of concurrent durvalumab/radiotherapy, radiographic assessment with CT chest with contrast including adrenals will occur within 2 weeks. Further radiographic assessment will occur every 3 months for 2 years. After 2 years, radiographic disease assessment should be performed every 6 months during year 3-5 then annually thereafter. FDG-PET/CT should be done to confirm clinically uncertain progression or treatment related effects at the discretion of the treating investigator. This imaging may be done locally.

<sup>3At 6 months only.

<sup>4At 12 weeks and end of the study.

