# **STUDY SCHEMA**

# **STUDY SUMMARY**

	Single arm, Phase II trial of concurrent Durvalumab (MEDI 4736) and
Title	radiotherapy followed by consolidative Durvalumab (MEDI 4736) for Stage III Non-Small Cell Lung Cancer (NSCLC)
Short Title	TBD
Protocol Number	STU-2019-1082
Phase	Phase 2
Methodology	Open label
Study Duration	4 years
Study Center(s)	Single-center
Objectives	12-month progression-free survival (PFS) rate based on an assessment by an investigators according to RECIST 1.1 criteria
Number of Subjects	50
Diagnosis and Main Inclusion Criteria	Stage III non-small cell lung cancer Zubrod 0 or 1
Study Product(s), Dose, Route, Regimen	Durvalumab/MEDI 4736 1500mg every 4 weeks [Q4W] intravenous during concurrent radiotherapy, 1500mg every 4 weeks [Q4W] intravenous [IV] up to one year during consolidative phase. Thoracic RT 60 Gy/30F
Duration of administration	1 year
Reference therapy	Concurrent chemo-radiation
Statistical Methodology	Progression-free survival and overall survival will be estimated using the Kaplan-Meier approach and the corresponding confidence intervals will be estimated using Greenwood's formula. Distant metastases-free survival, local and regional control will be estimated using the Kaplan-Meier approach.

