### 2.4 Endpoints

- 2.4.1 Primary endpoint of 12-month progression-free survival (PFS) rate is based on an assessment by an investigators according to RECIST 1.1 criteria; PFS is defined as the time from the study enrollment to documented progressive disease or death due to any cause, whichever occurs first;
- 2.4.2 Secondary endpoint of safety and tolerability will be assessed by adverse event according to CTCAE V.5;
- 2.4.3 Secondary endpoint of overall survival is defined as the time from study enrollment to death due to any cause;
- 2.4.4 Secondary endpoint of distant metastases free survival is defined as the time from the study enrollment to any new distant lesion;
- 2.4.5 Secondary endpoint of local and regional control defined as the time from the study enrollment to any local and regional lesion;
- 2.4.6 Exploratory endpoint of biomarker and biomarker correlatives;
- 2.4.7 Exploratory endpoint of proportion of patients alive at 12 and 24 months.

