**Delivery Compliance Criteria** 

Delivery Compliance Criteria		
	Per Protocol	Variation
		Acceptable
Start date (days after step 1 registration)	14 days	15-30 days
RT Elapsed Days	< 45 days	46-51 days
Interruptions (other than holidays or weekends)	0-2 days	3-7 days

**Note**: Cases will be scored as Deviation Unacceptable when the time limits given above are not met.

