## 4.6 Duration of Follow Up

Subjects will be followed every 3 months until 2 years post concurrent durvalumab/RT then every 6mos during year 3-5, then yearly or until death, whichever occurs first.

Subjects who discontinue for reasons other than progressive disease will have post-treatment follow-up for disease status until disease progression, initiating a non-study cancer treatment, withdrawing consent or becoming lost to follow-up. After documented disease progression each subject will be followed for overall survival until death, withdrawal of consent, or the end of the study (whichever occurs first). Subjects removed from treatment for unacceptable adverse events will be followed until resolution or stabilization of the adverse event.

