#### 10.2 Accrual

In the PACIFIC trial, patients who received consolidative durvalumab after chemoradiation had a 12-month PFS rate of 55%. PFS was measured starting after completion of chemoradiation, when anti-PDL1 treatment was started. This represents the assumed performance of the experimental arm in this study. We recognize that all patients who were randomized in the PACIFIC trial had tolerated and not progressed on chemoradiation, which represents some degree of selection bias. The possibility of early progression or treatment intolerance were taken into account when selecting the margins for the non-inferiority design of this study. A sample size of 47 achieves 80% power to detect a non-inferiority against an upper hazard ratio of 1.4 using a log-rank test at a 0.1 significance level when the actual hazard ratio is 1.0 and the standard of care group hazard rate is 0.5978 (which is equal to 1-year PFS rate of 55% using an exponential model). Three additional patients will be enrolled (total N=50) to account for 5% loss to follow-up. Patients will be accrued for a period of 3 years with 1-year follow-up.

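### Scans are timed from the end of radiotherapy while PFS runs from enrolment, so almost no patient has a scan due at 12 months and the Kaplan-Meier 12-month rate reads about 2 to 4 points above underlying PFS

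*Combined protocol and SAP*

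**What the plan says.** Section 2.4, repeated in 10.1.2, sets the clock for the primary endpoint: "PFS is defined as the time from the study enrollment to documented progressive disease or death due to any cause, whichever occurs first". The endpoint is the rate at 12 months.

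The imaging clock is in section 5.4. Footnote 2 of the consolidative table and footnote 1 of the follow-up table state that after concurrent treatment "radiographic assessment with CT chest with contrast including adrenals will occur within 2 weeks", followed by "Further radiographic assessment will occur every 3 months for 2 years". Section 4.6 uses the same anchor: "Subjects will be followed every 3 months until 2 years post concurrent durvalumab/RT".

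The Delivery Compliance Criteria in section 4.4.8 link the two clocks. Radiotherapy starts 14 days after registration per protocol, with 15 to 30 days acceptable. It lasts under 45 days per protocol, with 46 to 51 acceptable. The Study Summary gives the course as "Thoracic RT 60 Gy/30F".

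Section 10.3.1 plans Kaplan-Meier estimation of PFS with Greenwood intervals. The documents contain no scan at 12 months from enrolment, no window for the CT scans, no rule for dating progression that arises between scans, and no interval-censored analysis.

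**The concern.** A landmark rate estimated by Kaplan-Meier depends on when disease is looked for just before the landmark. If the last scan is at month 10.8 and the next at month 13.8, progression that arises in month 11 or 12 and is not detected clinically before the next scan is dated after month 12. It is therefore absent from the 12-month estimate. For events found by scheduled scans, this error can only raise the rate.

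The 12-month rate is the trial's single primary objective, and there is no concurrent arm that would share the lag. The non-inferiority hazard ratio of 1.4 corresponds to a 12-month PFS of 43.3%, which is 11.7 points below 55%. A few points on the primary estimate are therefore not negligible.

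**Working it through.** **The plan's own figures.** -ln(0.55) = 0.5978 per year, as section 10.2 states, so S(t) = exp(-0.5978 t/12) with t in months, and S(12) = 55.0%. At a hazard ratio of 1.4, S(12) = exp(-0.8369) = 43.3%. The sample size reproduces as a one-sample log-rank design at one-sided 0.1:
- Events = (1.2816 × √1.4 + 0.8416)² / 0.4² = 34.75.
- Event probability with 3 years' accrual and 1 year's follow-up = 0.744.
- N = 34.75/0.744 = 46.7, so 47.

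The design test is thus a log-rank test, not a test of the 12-month Kaplan-Meier rate.

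**Last scan before month 12.** L = (days to radiotherapy start + radiotherapy days + days to post-radiotherapy scan)/30.44 + 9 months. The text does not say whether the 3-month steps run from the end of radiotherapy or from the first scan. In the first case, the days to the post-radiotherapy scan drop out of L. Radiotherapy of 42 days is used as typical for 30 fractions.

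**Overstatement.** If every progression is found only at a scheduled scan, Kaplan-Meier at month 12 reads S(L), so the overstatement is S(L) - S(12).

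| Start day, RT days, first scan | L (months) | Next scan | S(L) - S(12) |
|---|---|---|---|
| 14, 42, +0 (or steps from RT end) | 10.84 | 13.84 | 3.3 points |
| 14, 42, +7, steps from first scan | 11.07 | 14.07 | 2.6 |
| 14, 42, +14, steps from first scan | 11.30 | 14.30 | 2.0 |
| Immediate start, 40, +0 | 10.31 | 13.31 | 4.8 |
| 30, 45, +14, steps from first scan | 11.92 | 14.92 | 0.2 |
| 30, 51, +14, steps from first scan | 9.12 | 12.12 | 8.5 |

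For example, S(10.84) = exp(-0.5400) = 58.3%, against 55.0%.

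**Averages.** Timing is taken as uniform over each range and the first scan as uniform over 0 to 14 days. Each range below covers both anchors.
- Start on days 1 to 14, radiotherapy 40 to 45 days: L lies between days 315 and 347. The overstatement is 3.2 to 3.8 points, or 2.5 to 3.1 if 20% of events are seen without a scheduled scan.
- Start on days 1 to 30, radiotherapy 40 to 51 days: 2.2 to 2.8 points, or 1.7 to 2.2 with 20% seen off-schedule.
- If half of events are seen off-schedule: about 0.9 to 2.0 points across these timing ranges.

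**How often a scan falls near month 12.** Under the per-protocol ranges, none falls within a week before it. Over the full allowed range this happens in about 5% of schedules, and only if steps are counted from the first scan.

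**After the change.** With the third 3-monthly scan at month 12, L = 12 and the reading returns to 55.0%.

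**The case against.** Four objections deserve an answer.

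*The endpoint is time to documented progression, so Kaplan-Meier on documentation dates estimates it as defined.* This is correct as a matter of definition, and every scan-based trial has some lag. It still leaves a 12-month rate that depends on where the scan grid happens to fall. The size of that effect varies with radiotherapy start and duration, which have nothing to do with disease control.

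*The benchmark was presumably scan-based too.* This stands. The documents do not give that trial's imaging schedule, so the net bias against 55% cannot be computed. A reader might infer that the comparison with 55% is tilted upward by the full 2 to 4 points. The documents do not support that.

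*The error rate.* A reader might also infer that the type I error exceeds its nominal 10%. Such a figure would require a test of the 12-month Kaplan-Meier rate, which the plan does not specify, and a benchmark free of lag, which cannot be shown. Section 10.2 cites a log-rank test over all follow-up. Re-timing scans does not correct that test, because with roughly 3-monthly scans the average detection lag stays near half an interval.

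*Progression may be found between scans.* The plan has examinations at each monthly infusion and FDG-PET/CT for uncertain findings. This lowers the figure, which is why the 50% off-schedule case is shown. It does not bring it to zero.

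**Conclusion.** The point holds as a mismatch between the PFS clock and the imaging clock. Almost no patient has a scan due at 12 months from enrolment. To say that none does would go too far, because a late start with a long radiotherapy course can bring one close.

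The Kaplan-Meier 12-month rate reads about 2 to 4 points above underlying PFS, and about 1 to 2 points if half of events are found off-schedule. This rests on the protocol's exponential hazard of 0.5978, on radiotherapy timing within the stated compliance limits, and on an assumed share of off-schedule detection. For scale, 2 to 4 points is about 17% to 34% of the 11.7-point distance between 55% and 43.3%.

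The conclusion concerns the trial's own reported rate. It makes no claim about net bias against the benchmark or about the operating characteristics of the log-rank test. The repair is cheap and worth making.

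**What to change.** 1. In both imaging footnotes of section 5.4, keep the post-radiotherapy scan and time the next three so that the third falls at 12 months from enrolment.
2. Either give that scan a window that closes at the 12-month cut, or state in section 10.3.1 that progression found at it is assigned to the nominal month-12 date in the 12-month estimate. One of the two is needed. If the scan falls just after day 365 and its actual date is used, the previous scan lies 98 to 103 days earlier for a day-14 start. The overstatement for that patient is then about 10 points: exp(-0.5978 × 262/365) - 0.55 = 0.101.
3. Add an interval-censored sensitivity analysis of PFS.

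**Cost.** There are no extra scans. With the post-radiotherapy scan on days 56 to 70, each of the three intervals is (365 - 56)/3 = 103 to (365 - 70)/3 = 98 days, against about 91 now. The longest is about 108 days. That is roughly 1 to 2.5 weeks longer for most patients, and no longer for the latest starters.

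Fixing scans at months 6, 9 and 12 is less attractive. For per-protocol starts, the first interval would run to about 110 to 142 days, some 3 to 7 weeks longer than 3 months. Section 1.4 describes the first year after chemoradiation as the period of highest risk.

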#### **ASSESSMENTS IN FOLLOW UP**

Assessments	Every 3 mos until 2 years post concurrent durvalumab/RT then every 6mos during year 3-5, then yearly
History and physical exam	Х
Zubrod performance status	Х
Tumor Measurement	Х
Med Onc exam	Х
AE Evaluation	Х
CBC, BMP	X
CT Chest with contrast and include adrenals	X 

¹After completion of concurrent durvalumab/radiotherapy, radiographic assessment with CT chest with contrast including adrenals will occur within 2 weeks. Further radiographic assessment will occur every 3 months for 2 years. After 2 years, radiographic disease assessment should be performed every 6 months during year 3-5 then annually thereafter. FDG-PET/CT should be done to confirm clinically uncertain progression or treatment related effects at the discretion of the treating investigator. This imaging may be done locally.

#### 5.5 Removal of Subjects from Study

Subjects can be taken off the study treatment and/or study at any time at their own request, or they may be withdrawn at the discretion of the investigator for safety, behavioral or administrative reasons. The reason(s) for discontinuation will be documented and may include:

- 5.5.1 Subject voluntarily withdraws from treatment (follow-up permitted);
- 5.5.2 Subject withdraws consent (termination of treatment and follow-up);
- 5.5.3 Subject is unable to comply with protocol requirements;
- 5.5.4 Subject demonstrates disease progression (unless continued treatment with study drug/treatment is deemed appropriate at the discretion of the investigator);
- 5.5.5 Subject experiences toxicity that makes continuation in the protocol unsafe;
- 5.5.6 Treating physician judges continuation on the study would not be in the subject's best interest;
- 5.5.7 Subject becomes pregnant (pregnancy to be reported along same timelines as a serious adverse event):
- 5.5.8 Development of second malignancy (except for basal cell carcinoma or squamous cell carcinoma of the skin) that requires treatment, which would interfere with this study;
- 5.5.9 Lost to follow-up. If a research subject cannot be located to document survival after a period of 2 years, the subject may be considered "lost to follow-up." All attempts to contact the subject during the two years must be documented and approved by the Data Monitoring Committee.

#### 5.6 Study Restrictions

#### Female patient of child-bearing potential

Female patients of childbearing potential who are not abstinent and intend to be sexually active with a non-sterilized male partner must use at least 1 highly effective method of contraception from the time of screening throughout the total duration of the drug treatment and the drug washout period (90 days after the last dose of durvalumab monotherapy). Non-sterilized male partners of a female patient of childbearing potential must use male condom plus spermicide throughout this period. Cessation of birth control after this point should be discussed with a responsible physician. Periodic abstinence, the rhythm method, and the withdrawal method are not acceptable methods of birth control. Female patients should also refrain from breastfeeding throughout this period.

#### Male patients with a female partner of childbearing potential

Non-sterilized male patients who are not abstinent and intend to be sexually active with a female partner of childbearing potential must use a male condom plus spermicide from the time of screening throughout the total duration of the drug treatment and the drug washout period (90 days after the last dose of durvalumab monotherapy). However, periodic abstinence, the rhythm method, and the withdrawal method are not acceptable methods of contraception. Male patients should refrain from sperm donation throughout this period.

Female partners (of childbearing potential) of male patients must also use a highly effective method of contraception throughout this period.

Females of childbearing potential are defined as those who are not surgically sterile (ie, bilateral salpingectomy, bilateral oophorectomy, or complete hysterectomy) or post-menopausal.

Women will be considered post-menopausal if they have been amenorrheic for 12 months without an alternative medical cause. The following age-specific requirements apply:

- Women <50 years of age would be considered post-menopausal if they have been amenorrheic for 12 months or more following cessation of exogenous hormonal treatments and if they have luteinizing hormone and follicle-stimulating hormone levels in the post-menopausal range for the institution.
- Women ≥50 years of age would be considered post-menopausal if they have been amenorrheic for 12 months or more following cessation of all exogenous hormonal treatments, had radiation-induced menopause with last menses >1 year ago, had chemotherapy-induced menopause with last menses >1 year ago.

Highly effective methods of contraception, defined as one that results in a low failure rate (ie, less than 1% per year) when used consistently and correctly are described in Table 2. Note that some contraception methods are not considered highly effective (e.g. male or female condom with or without spermicide; female cap, diaphragm, or sponge with or without spermicide; non-copper containing intrauterine device; progestogen-only oral hormonal contraceptive pills where inhibition of ovulation is not the primary mode of action [excluding Cerazette/desogestrel which is considered highly effective]; and triphasic combined oral contraceptive pills).

#### **Table 1. Highly Effective Methods of Contraception (<1% Failure Rate)**

Barrier/Intrauterine methods	
 
Hormonal Methods
 

Copper T intrauterine device     Levonorgestrel-releasing intrauterine system (e.g., Mirena®) a	
 
Hormonal Methods
 
Implants: Etonogestrel-releasing implants: e.g. Implanon® or Norplant®
 
Intravaginal:         Ethinylestradiol/etonogestrel-releasing intravaginal devices: e.g. NuvaRing®
 
Injection: Medroxyprogesterone injection: e.g. Depo-Provera®
 
Combined Pill: Normal and low dose combined oral contraceptive pill
 
Patch:         Norelgestromin/ethinylestradiol-releasing transdermal system: e.g.         Ortho Evra®
 
Minipillc: Progesterone based oral contraceptive pill using desogestrel: Cerazette® is currently the only highly effective progesterone-based
 

#### **Blood donation**

Patients should not donate blood while participating in this study or for at least 90 days following the last infusion of durvalumab.

#### 6.0 Measurement of Effect

**Antitumor Effect** 

Response and progression will be evaluated in this study using the new international criteria proposed by the Response Evaluation Criteria in Solid Tumors (RECIST v 1.1) Committee [Eur J Cancer. 2009;45(2):228-247]. Changes in only the largest diameter (unidimensional measurement) of the tumor lesions are used in the RECIST v1.1 criteria.

#### 6.1.1 Definitions

Evaluable for toxicity. All subjects will be evaluable for toxicity from the time of their first treatment with study therapy.

Evaluable for objective response. Only those subjects who have measurable disease present at baseline, have received at least one cycle of therapy, and have had their disease re-evaluated will be considered evaluable for response. These subjects will have their response classified according to the definitions stated below. (Note: Subjects who exhibit objective disease progression prior to the end of cycle 1 will also be considered evaluable.)

#### 6.1.2 Disease Parameters

Measurable Disease: Tumor lesions: Must be accurately measured in at least one dimension (longest diameter in the plane of measurement is to be recorded) with a minimum size of:

- 1. 10 mm by CT scan (CT scan slice thickness no greater than 5 mm)
- 2. 10 mm caliper measurement by clinical exam (lesions which cannot be accurately measured with calipers should be recorded as non-measurable)
- 3. 20 mm by chest x-ray.

Malignant lymph nodes: To be considered pathologically enlarged and measurable, a lymph node must be ≥ 15 mm in short axis when assessed by CT scan (CT scan slice thickness recommended to be no greater than 5 mm). Lymph nodes merit special mention since they are normal anatomical structures which may be visible by imaging even if not involved by tumor. Pathological nodes which are defined as measurable and may be identified as target lesions must meet the criterion of a short axis of ≥ 15 mm by CT scan. Only the short axis of these nodes will contribute to the baseline sum. The short axis of the node is the diameter normally used by radiologists to judge if a node is involved by solid tumor. Nodal size is normally reported as two dimensions in the plane in which the image is obtained (for CT scan this is almost always the axial plane; for MRI the plane of acquisition may be axial, sagittal or coronal). The smaller of these measures is the short axis. For example, an abdominal node which is reported as being 20 mm x 30 mm has a short axis of 20 mm and qualifies as a malignant, measurable node. In this example, 20 mm should be recorded as the node measurement. All other pathological nodes (those with short axis ≥ 10 mm but < 15 mm) should be considered non-target lesions. Nodes that have a short axis < 10 mm are considered non-pathological and should not be recorded or followed.

Note: Previously irradiated lesions are non-measurable except in cases of documented progression of the lesion since the completion of radiation therapy.

